**Study 111-301 Statistical Analysis Plan**

2-sided p-value. In the event that the height Z-score endpoint test is positive, the testing on this key secondary endpoint is considered to be confirmatory. The endpoint is considered positive if the 2-sided p-value in favor of BMN 111 is < 0.05 .

This analysis will be repeated on the Per Protocol population. In addition, the sensitivity and supplementary analyses of upper to lower body segment ratio [described in Section 14.3.3] will be performed using the FAS population.

A line plot of the mean (\pm SD) upper to lower body segment ratio will be presented at ≥ 12 Months Prior, ≥ 6 Months Prior, Baseline, Week 26 and Week 52 time points by treatment group.

All upper to lower body segment ratios will be listed alongside the standing and sitting height.

14.5 Other Secondary Efficacy Endpoint(s)

Any p-values resulting from analyses of these secondary efficacy endpoints are non-confirmatory.

14.5.1 Body Proportion Ratios

Body measurements are taken at Screening, Day 1, Week 13, Week 26, Week 39, and Week 52. Each of the body proportion ratios below will be calculated to 2 decimal places.

- Upper Arm Length to Lower Arm (Forearm) Length Ratio
- Upper Leg Length (Thigh) to Knee to Heel Length Ratio
- Upper Leg Length (Thigh) to Tibial Length Ratio
- Arm Span to Standing Height Ratio

The absolute values at ≥ 12 Months Prior, ≥ 6 Months Prior, Baseline, Week 26 and Week 52, and change from baseline at Week 26 and Week 52 will be summarized (n, mean, SD, median, 25th and 75th percentile, minimum, maximum) and presented by treatment group.

A line plot of the mean (\pm SD) each body proportion ratio will be presented at ≥ 12 Months Prior, ≥ 6 Months Prior, Baseline, Week 26 and Week 52 time points by treatment group.

Box plots of each ratio at Week 52 will be provided by treatment group.

All assessments will be listed by treatment group, subject and visit.

Study 111-301 Statistical Analysis Plan

Analysis:

No imputation will be applied for missing Week 52 assessments. Analyses will be based on observed data only, and SAS PROC MIXED will be used to test the null hypothesis of no treatment difference using an ANCOVA model described below, for each of the above **body proportion ratios**.

PROC MIXED;

CLASS Stratum Treatment;

MODEL Change from baseline in **body proportion ratio** at Week 52 =
Baseline_ **body proportion ratio** Baseline_Age Baseline_AGV Baseline_Height_Z-
score Treatment Stratum;

LSMEANS Treatment /DIFF = control (“Placebo”) CL;

RUN;

For each body proportion ratio, the least-squares (LS) mean change from baseline at Week 52 will be presented for each treatment group, along with the difference in LS means (calculated as BMN 111 – Placebo), the 95% confidence interval for the difference, and 2-sided p-value.

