**Study 111-301 Statistical Analysis Plan****5 GENERAL ANALYSIS CONSIDERATIONS**

The analyses described in this SAP are based on Amendment 4 of the protocol (dated 01-February-2019).

Individual subject data that is reflected in data summaries will be provided in **PI**. Unless otherwise specified, all **PI** will be by treatment group and ordered by subject number, where subject number includes the site number.

Summary tables and figures are provided by treatment group with no overall population column. There are certain exceptions (e.g. subject disposition, demographics, baseline characteristics and safety data) which are indicated in the relevant sections.

Baseline annualized growth velocity (AGV) is defined in Section 14.3.1. Baseline growth measures (other than AGV) and baseline weight are those assessed on Day 1 of dosing, regardless of timing relative to dosing. (Note: If no assessments are available, then the baseline assessment will be the last non-missing assessment prior to Day 1). All other baseline assessments are the last non-missing on-study 301 assessments prior to administration of study drug. Change from baseline is calculated as: [post-baseline value – baseline value]; Percent change from baseline is calculated as: ([post-baseline value – baseline value]/baseline value) x 100.

The Screening visit will not be presented in descriptive summaries over time. When the analysis windows have been applied (see Section 5.4), data collected at the screening visit may be included in the Baseline assessment. All assessments will be listed, but only those assessments assigned to visits according to the windows applied (see Section 5.4) will be summarized in tables or graphically. Exceptions to this are summaries of the worst post-baseline laboratory data in shift tables where all assessments are considered, and also the standing height assessments displayed in the spaghetti plots.

Unless otherwise specified, the number of subjects, mean, 25th percentile, median, 75th percentile and estimates of precision (e.g. SD, confidence interval) will be displayed to one more decimal place than the collected data. Minimum and maximum values will be presented to the same decimal places as the collected data. For summaries by visit, the number of subjects with non-missing observations (n) according to the analysis windows (see Section 5.4 for further details) at the derived visit will be presented.

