13 EXTENT OF EXPOSURE TO STUDY DRUG

Dosing information is recorded by subjects (in the paper diary) and also by the site on visit days. In the case of duplicate records with the same date, if the investigator confirms the date, then investigator reported dosing data will be used. All summaries will be based on the safety population, and presented by treatment group.

The day of the first dose of study drug is referred to as Day 1. A missed dose is defined as a calendar day without a dose between the date of Day 1 and date of last dose.

Descriptive statistics will be provided for the following variables:

- Duration of treatment (days)
 - = Date of last dose – Date of first dose + 1
- Total number of doses administered
 - = Number of doses administered between date of Day 1 and date of last dose
- Total number of doses missed
 - = Number of doses missed between date of Day 1 and date of last dose
- Total amount of weight adjusted dose administered (ug/kg)
- Average weight-adjusted daily dose administered (ug/kg/day)

The frequency and percent of subjects will be provided for the following variables, where missed doses are counted between the date of first dose (Day 1) and date of last dose:

- Number of subjects who missed at least one dose
- Number of subjects who missed more than one dose
- Number of subjects who missed more than 5 consecutive doses
- Number of subjects who missed more than 10 consecutive doses

The frequency and percent of all missed doses will be provided for the following variable:

- Reason for missed dose (Site Error, Parent/Caregiver Error, Home Health Error, Adverse Event, Other, Missing).

PI

**Study 111-301 Statistical Analysis Plan****14 EFFICACY EVALUATIONS****14.1 General Approaches for Analyzing Growth Parameters**

All growth parameters assessed by anthropometric measurements are measured at Day 1, Week 13, Week 26, Week 39 and Week 52.

Growth parameters are measured 3 times for each assessment. It is the mean of these 3 assessments that are considered for the summaries and analyses. In the event that all 3 are not available, the mean of the 2, or the individual assessment is taken.

All efficacy endpoints will be assessed using the FAS. In addition, the primary and key secondary endpoints (AGV, height Z-score, and upper to lower body segment ratio) will also be assessed using the PP population.

Estimand formulations are provided for the primary and key secondary endpoints.

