14.4.2 Upper to Lower Body Segment Ratio

Standing height and sitting height are measured at Screening, Day 1, Week 13, Week 26, Week 39, and Week 52.

The upper to lower body segment ratio will be calculated at each visit as follows:

$$\text{Upper to Lower Body Segment Ratio} = \frac{\text{Sitting height}(cm)}{\text{Standing height}(cm) - \text{Sitting height}(cm)}$$

The upper to lower body segment ratio at Baseline, Week 26 and Week 52, and its change from baseline at Week 26 and Week 52 will be summarized (n, mean, SD, median, 25th and 75th percentile, minimum, maximum) and presented by treatment group. Figures will be provided as described in Section 14.1.

The following key secondary hypothesis will be tested (two-tailed):

Study 111-301 Statistical Analysis Plan

H₀: Difference in mean upper:lower body segment ratio change from baseline at week 52 between BMN 111 group and the placebo group = 0

H_a: Difference in mean upper:lower body segment ratio change from baseline at week 52 between BMN 111 group and the placebo group ≠ 0

The upper to lower body segment ratio will be analyzed using the same methods and estimand formulation as the primary analysis. The primary analysis of the upper to lower body segment ratio will be assessed on the FAS. If MI methods are used to impute Week 52 results for the primary endpoint (AGV), then the same MI approach will be used to impute missing Week 52 upper to lower body segment ratios. Missing sitting height at Week 52 will be imputed in the same manner as missing standing height, using PROC MI. Missing upper to lower body segment ratios Week 52 will be calculated from the imputed values for sitting and standing height. The difference between the BMN 111 group and the placebo group in the mean change from baseline in the upper:lower body segment ratio at Week 52 will be tested based on 10 imputed data sets.

If multiple imputation is not applied for the primary endpoint, then missing sitting height and standing height at Week 52 will be imputed by applying the baseline AGV for sitting height and standing height to the last available sitting/standing height assessment (as described in Section 14.3.2). Based on this imputed sitting height and standing height at Week 52, the upper:lower body segment ratio will be calculated, and the model described above will then be applied at Week 52.

SAS PROC MIXED will be used to test the null hypothesis using an ANCOVA model described below.

PROC MIXED;

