16.3.1 Vertebral Height

Vertebral heights (anterior, medial, and posterior) will be measured for each individual vertebra (L1, L2, L3, L4, and L5).

The following ratios will be calculated for each individual vertebra (L1, L2, L3, L4, and L5) and reported to 1 decimal place:

- Anterior height (cm) to medial height (cm)
- Anterior height (cm) to posterior height (cm)
- Medial height (cm) to posterior height (cm)

For each of the above ratios, the absolute values at Baseline and Week 52, and change from baseline at Week 52 will be summarized (n, mean, SD, median, 25th and 75th percentile, minimum, maximum) and presented by treatment group.

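### Extremity ratios are rounded to 2 decimals before they are tested, and vertebral ratios are reported to only 1: small, avoidable rounding error in non-confirmatory endpoints

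*SAP*

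**What the plan says.** **Extremity ratios (SAP 14.5.1).** Four ratios are covered: upper arm to forearm, thigh to knee-to-heel, thigh to tibia, and arm span to standing height. The rule is "Each of the body proportion ratios below will be calculated to 2 decimal places". The verb is about calculation, not presentation. The model line in the same section begins "MODEL Change from baseline in body proportion ratio at Week 52", with the baseline ratio among the covariates. SAP 14.5 sets the status of these tests: "Any p-values resulting from analyses of these secondary efficacy endpoints are non-confirmatory".

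**Vertebral height ratios (SAP 16.3.1).** Three ratios are formed for each of L1 to L5, "and reported to 1 decimal place". Then: "For each of the above ratios, the absolute values at Baseline and Week 52, and change from baseline at Week 52 will be summarized". No test is planned.

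**Related rules.** SAP 5 says that means, quartiles and measures of precision "will be displayed to one more decimal place than the collected data", which governs display only. For the key secondary ratio, SAP 14.4.2 says "The upper to lower body segment ratio will be calculated at each visit as follows" and gives a formula with no rounding instruction. SAP 14.1 adds "Growth parameters are measured 3 times for each assessment", and the mean of the readings feeds the analyses.

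**The concern.** A ratio rounded at baseline and again at Week 52 puts two rounding errors into every change score. Those errors are pure noise, and the plan gives no reason for accepting them. They also give back part of the precision that triplicate measurement is meant to buy. The extremity ratios differ in this respect from the upper-to-lower ratio, which has no such rule.

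For the vertebral ratios the step is ten times larger. They are there to show change in vertebral shape, and a grid of 0.1 may be too coarse for that. Both sets serve secondary objectives (Protocol 8): body proportion of the extremities, and bone morphology.

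**Working it through.** **The plan's own figure.** The documents state no SD, precision or power for any ratio. The only figure to reproduce is the primary power: 55 per arm, difference 1.75 cm/year, SD 2.80, two-sided 0.05, stated as about 90%. The normal approximation gives 90.6% and the noncentral t with 108 df gives 90.1%, so it reproduces. The same 55 per arm is used below.

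**Formulas.** Rounding to a step h gives an error SD of h/√12 per value. A change between two independently rounded values has error SD √2 × h/√12 = h/√6. The relative increase in variance is (h²/6)/SD², where SD is that of the true change. The SE grows by the square root of 1 plus that increase.

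**Two decimals (h = 0.01).** Error SD is 0.0029 per value and 0.01/√6 = 0.0041 per change. In quadrature, this adds 0.0041 × √(2/55) = 0.0008 to the SE of the treatment difference. The power column takes the effect that would have 90% power without rounding, 3.24 × SD × √(2/55).

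| Assumed SD of change | Extra variance | SE factor | Power after rounding |
|---|---|---|---|
| 0.01 | 16.7% | 1.080 | 85.1% |
| 0.015 | 7.4% | 1.036 | 87.9% |
| 0.02 | 4.2% | 1.021 | 88.8% |
| 0.03 | 1.9% | 1.009 | 89.5% |
| 0.04 | 1.0% | 1.005 | 89.7% |
| 0.05 | 0.7% | 1.003 | 89.8% |

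**Simulation check.** 5,000 trials per case, 55 per arm, t-test on change, baseline ratio with mean 1.0 and SD 0.06 (assumed). At SD 0.02 the mean treatment difference was 0.0123 with and without rounding, and power was 88.8% unrounded against 87.4% rounded. At SD 0.01, power was 89.5% against 84.9%. Type I error after rounding was 4.8% to 5.1%. The planned model is an ANCOVA, so the SD in the table is best read as the residual SD of change.

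**Physical scale.** If segments are 12 to 25 cm long (assumed), a 0.1 cm shift in one segment moves a ratio near 1 by 0.1/25 = 0.004 to 0.1/12 = 0.008, a little under one rounding step. For lengths near 100 cm (assumed, for arm span to standing height), 0.1 cm moves the ratio by 0.001, so one step corresponds to about 1 cm.

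**One decimal (h = 0.1), only if change is formed from rounded values.** Error SD is 0.029 per value and 0.1/√6 = 0.041 per change. Recorded changes can then only be multiples of 0.1.

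| Assumed SD of change | SE factor, formula | SE factor, simulated | Changes recorded as exactly 0 (simulated) |
|---|---|---|---|
| 0.02 | 2.27 | 0.0394/0.0199 = 1.98 | 83% |
| 0.03 | 1.69 | 0.0485/0.0298 = 1.63 | 74% |
| 0.05 | 1.29 | 0.0641/0.0497 = 1.29 | 58% |

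At the smaller SDs the formula overstates the loss. When the change is small against the step, the two rounding errors are no longer independent.

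**One decimal, display only.** Change is computed at full precision, but an individual change smaller than 0.05 in size prints as 0.0.

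**The case against.** The best case for the plan has four parts.

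1. The word calculated may be loose wording for presented. That is possible, but the text does not say so, and the display rule in SAP 5 does not override a rule about calculation. A programmer could follow it literally.

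2. The effect at 2 decimals is small. This stands. At an assumed SD of change of 0.02 or more the loss is about 1 power point, and about 5 points needs an SD near 0.01, the bottom of the range.

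3. Nothing is lost from the record. The component lengths are analysed in centimetres without any ratio rounding and are listed by subject and visit (SAP 14.5.2), so the extremity ratios can be recomputed. This stands, but it does not correct the planned tables.

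4. Reported, in SAP 16.3.1, most naturally means display. If 1 decimal is then treated as the data precision, SAP 5 would give means and quartiles a second decimal, so a mean change of 0.04 would still print as 0.04. That is a fair reading. SAP 16.3.1 does not settle it, and individual values, minima and maxima would remain at 1 decimal.

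Three stronger readings are tempting, and the documents do not support them. A reader might infer that rounding hides a treatment effect on the extremity ratios. It does not: it adds noise without shifting the mean difference. A reader might infer that the trial's main conclusions are affected. They are not: the extremity tests are non-confirmatory and the key secondary ratio has no rounding rule. A reader might also take the variance inflation at 1 decimal as established. It depends on an order of operations that the SAP does not state, and no test is run on those ratios.

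**Conclusion.** The point holds as a minor one, in two parts of different standing.

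- **SAP 14.5.1:** as written, rounding precedes analysis and adds avoidable error to four non-confirmatory endpoints. The size depends wholly on an SD of change that the documents do not give: negligible at 0.03 and above, and material only near 0.01.
- **SAP 16.3.1:** this is an ambiguity rather than a demonstrated flaw. If change is taken from rounded ratios, most individual changes would be recorded as 0 over an assumed SD of 0.02 to 0.05. If rounding is for display only, the summaries may still be too coarse. Both statements assume vertebral ratios near 1.

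This is a free improvement, not a threat to the trial's conclusions.

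**What to change.** In SAP 14.5.1, replace the rounding rule with a statement that ratios and their changes from baseline are derived at full precision from the averaged measurements and rounded only for display. In SAP 16.3.1, say the same for the vertebral ratios. Set display precision so that the expected change is visible, for example 3 decimals for body proportion ratios and at least 2 for vertebral ratios. The exact number of decimals is a formatting choice; deriving before rounding is the substance.

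The cost is two wording edits. No new data are needed, and the confirmatory testing sequence does not change.

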14.5.2 Growth Measures

Each of the following anthropometric growth measures are recorded at Screening, Day 1, Week 13, Week 26, Week 39, and Week 52:

- Standing Height (cm)
- Sitting Height (cm)
- Upper Leg Length (Thigh) (cm)
- Knee to Heel Length (cm)
- Tibial Length (cm)
- Head Circumference (cm)
- Upper Arm Length (cm)
- Lower Arm (Forearm) Length (cm)
- Arm Span (cm)

In addition, a measure of lower body length will be calculated as follows:

- Lower Body Length (cm) = Standing height – Sitting height

Study 111-301 Statistical Analysis Plan

Baseline growth measures are those assessed on Day 1, regardless of timing relative to dosing. All summaries and analyses will be based on the FAS.

For each of the above growth measures (including lower body length), the absolute values at ≥ 12 Months Prior, ≥ 6 Months Prior, baseline, Week 26 and Week 52, and change from baseline at Week 26 and Week 52, will be summarized (n, mean, SD, median, 25th and 75th percentile, minimum, maximum) and presented by treatment group for each baseline age category (≥ 5 to < 8 , ≥ 8 to < 11 , ≥ 11 to < 15 , ≥ 15 to < 18 years).

Analysis:

Subjects with missing standing height at Week 52 will have standing height imputed, as described in Section 14.3.2. The same approach will be applied for missing sitting height assessments at Week 52.

With the exception of sitting height and standing height, no imputation will be applied for missing Week 52 assessments. Analyses will be based on observed data only.

For each growth measure, the null hypothesis of no difference between the BMN 111 group and the placebo group in the mean change from baseline at the Week 52 visit will be tested.

SAS PROC MIXED will be used to test the null hypothesis of no treatment difference using an ANCOVA model described below, for each of the above *growth measures*.

PROC MIXED;

CLASS Stratum Treatment;

MODEL Change from baseline in *growth measure* at Week 52 =
Baseline_*growth_measure* Baseline_AGV Baseline_Height_Z-score Treatment
Stratum;

LSMEANS Treatment /DIFF CL;

RUN;

For each growth measure, the least-squares (LS) mean change from baseline at Week 52 will be presented for each treatment group, along with the difference in LS means (calculated as BMN 111 – Placebo), the 95% confidence interval for the difference, and 2-sided p-value.

Spaghetti plots of standing height will be provided by treatment group and sex. These 8 plots will include age-sex specific reference ranges for average stature children (from the Centers for Disease Control and Prevention (CDC)) and age-sex specific reference ranges for short

Study 111-301 Statistical Analysis Plan

stature children (Hoover-Fong et al). All assessments will be included, including all height assessments collected in the 901 study up to the ≥ 12 months prior analysis visit.

All assessments will be listed by treatment group, subject and visit.

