4.6.2 Randomization Method

The centralized randomization with stratification is managed by an external vendor, using IXRS technology. Eligible subjects will be randomized whilst at the site, and receive their first dose of study drug on the same day.

In the original protocol, subjects were stratified based on sex and age (≤ 11 , > 11 years). At the time of protocol amendment 2, the strata were changed and subjects randomized after this time were stratified by sex and Tanner Stage. The original strata will be reported for all subjects; however all statistical analyses will reported as sex and Tanner Stage.

At least 110 eligible subjects will be stratified based on sex and Tanner Stage (Stage I, and $>$ Stage I) (with no greater than 20% of subjects $>$ Tanner Stage I), and randomly assigned in a 1:1 ratio to one of two treatment groups: placebo or BMN 111 at 15 $\mu\text{g}/\text{kg}$.

A separate stratified randomization scheme is in place for PI [REDACTED] subjects. This randomization scheme is set up to assure an overall approximate balance of PI [REDACTED] subjects randomized to both treatment arms. The subjects are stratified based on sex and Tanner Stage (Stage I, and $>$ Stage I), and in addition the blocks across the strata are sequenced to assure an overall balance across the treatment arms.

To achieve sex balance, approximately 50% of each sex will be enrolled, with neither to exceed 55%. For placebo and BMN 111, the route of administration is subcutaneous injection and the frequency is daily. Approximately 33 clinical centers worldwide were expected to participate in the study, with a cap of 11 subjects at each site.

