**Study 111-301 Statistical Analysis Plan**

- Week 52 (111-301).

Each table will include summaries of the absolute measures at each of these time points, and change from baseline at Week 26 and Week 52 (applying visit windows). The tables will summarize data by treatment group. These summaries are on continuous data and will include the number of subjects with assessments, mean, SD, median, 25th and 75th percentile, minimum and maximum.

Results of the statistical analyses will be provided in separate tables, including the least-squares (LS) mean change from baseline at Week 52 for each treatment group, the treatment difference in LS means (calculated as BMN 111 – Placebo), the 95% confidence interval (CI) for the treatment difference, and corresponding 2-sided p-value.

ANCOVA models will be used to determine the treatment difference at 52 weeks. Unless otherwise specified, all models include the following baseline covariates:

- Treatment group
- Stratum: (Male Tanner Stage I, Female Tanner Stage I, Male Tanner Stage >I, Female Tanner Stage >I)
- Age at baseline
- AGV at baseline
- Height Z-score at baseline

Note: If a subject is incorrectly assigned to a stratum at the time of randomization, they will be analyzed according to their actual sex and Tanner stage.

Subgroup analyses will only be performed for the primary analyses of the primary and key secondary endpoints (see Section 14.7).

PI will include the mean values used in analyses and summaries, and will be ordered by treatment group, subject and visit date. An additional PI of standing height will include all assessments (i.e., individual measures and means of the measures).

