Each of the 10 imputed datasets will be analyzed using an ANCOVA model that includes the following fixed-effect terms:

- Treatment group
- Stratum (Male Tanner Stage I, Female Tanner Stage I, Male Tanner Stage >I, Female Tanner Stage >I)

Study 111-301 Statistical Analysis Plan

- Baseline age
- Baseline AGV
- Baseline height Z-score

SAS PROC MIXED will be used to perform the analysis.

PROC MIXED;

CLASS Stratum Treatment;

MODEL Change from baseline in AGV at Week 52 = Baseline_Age Baseline_AGV
Baseline_Height_Z-Score Treatment Stratum;

LSMEANS Treatment / DIFF = control (“Placebo”) CL;

RUN;

For each imputed dataset, PROC MIXED will generate the least-squares (LS) mean change from baseline in AGV at Week 52 for each treatment group, along with the difference in LS means (calculated as BMN 111 – Placebo). PROC MIANALYZE will then be used to combine all of the estimates across the 10 imputed datasets in order to generate an overall estimate for each treatment group, and for the difference between treatment groups, with a 95% confidence interval for the difference and 2-sided p-value. The study will be considered positive if the 2-sided p-value in favor of BMN 111 is <0.05.

If there are less than 5 subjects with reference data as defined above then missing standing height at Week 52 (i.e. Day 365) will be imputed by applying the baseline AGV (cm/yr) to the last available height assessment as follows:

Standing Height at Day 365 =

$$\text{Last Assessed Height} + \frac{\text{AGV at Baseline}}{365.25} \times (365 - \text{Study Day of Last Height Assessment})$$

Based on this imputed standing height, the height z-score and AGV at Week 52 will be calculated. The ANCOVA model will then be applied to AGV at Week 52.

In the event that there are no subjects who discontinue treatment early with a missing assessment at Week 52 the ANCOVA model will be applied without any imputation.

This ANCOVA model analysis without imputation will be repeated on the PP population.

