14.4.1 Height Z-Score

Standing height is measured at Screening, Day 1, Week 13, Week 26, Week 39, and Week 52. Each measurement of standing height will be converted to an age-and sex-appropriate standard deviation score (SDS), also referred to as a Z-score, by comparison with reference data available for average stature children from the Centers for Disease Control and Prevention (CDC).

The following key secondary hypothesis will be tested (two-tailed):

H₀: Difference in mean height Z-score change from baseline at week 52 between BMN 111 group and the placebo group = 0

H_a: Difference in mean height Z-score change from baseline at week 52 between BMN 111 group and the placebo group ≠ 0

Height Z-score will be analyzed using the same methods and estimand formulation as the primary analysis. If multiple imputation is applied for testing the primary endpoint then the null hypothesis of no difference between the BMN 111 group and the placebo group in the mean change from baseline in the height Z-score at the Week 52 time point will also be tested based on 10 imputed data sets. Missing height Z-score at Week 52 will be calculated from the imputed standing height at this visit, as described for the primary endpoint. If multiple imputation is not applied for the primary endpoint, then the Week 52 height Z-score will be imputed as described above in Section 14.3.2.

SAS PROC MIXED will be used to test the null hypothesis using an ANCOVA model described below.

Study 111-301 Statistical Analysis Plan

PROC MIXED;

CLASS Stratum Treatment;

MODEL Change from baseline in Height Z-score at Week 52 = Baseline_Age
Baseline_AGV Baseline_Height_Z-score Treatment Stratum;

LSMEANS Treatment / DIFF= control (“Placebo”) CL;

RUN;

The least-squares (LS) mean change from baseline in height Z-score at Week 52 will be presented for each treatment group, along with the difference in LS means (calculated as BMN 111 – Placebo), the 95% confidence interval for the difference, and 2-sided p-value. In the event that the primary endpoint test is positive, the testing on the key secondary is considered to be confirmatory. The endpoint is considered positive if the 2-sided p-value in favor of BMN 111 is < 0.05.

This analysis will be repeated on the PP population, using the same approach as described for the primary endpoint. In addition, the sensitivity and supplementary analyses of height Z-score [described in section 14.3.3] will be performed using the FAS population.

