CLASS Stratum Treatment;

MODEL Change from baseline in upper:lower body segment ratio at Week 52 =
Baseline_Upper:Lower Body_Segment_Ratio Baseline_Age Baseline_AGV
Baseline_Height_Z-score Treatment Stratum;

LSMEANS Treatment /DIFF = control (“Placebo”) CL;

RUN;

The least-squares (LS) mean change from baseline in upper to lower body segment ratio at Week 52 will be presented for each treatment group, along with the difference in LS means (calculated as BMN 111 – Placebo), the 95% confidence interval for the difference, and

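### The growth-measure ANCOVA in SAP 14.5.2 leaves out baseline age, a default covariate in SAP 14.1 unless otherwise specified, without a stated reason; this can cost some precision for measures not closely tied to height.

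*SAP*

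**What the plan says.** SAP 14.1 sets the default: "Unless otherwise specified, all models include the following baseline covariates". The list that follows is treatment group, stratum (sex by Tanner stage), age, AGV and height Z-score.

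The SAP prints five PROC MIXED MODEL statements. Four follow the default on age:

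- 14.3.2, primary AGV: "MODEL Change from baseline in AGV at Week 52 = Baseline_Age Baseline_AGV"
- 14.4.1, height Z-score: "Change from baseline in Height Z-score at Week 52 = Baseline_Age"
- 14.4.2, upper-to-lower segment ratio: "Body_Segment_Ratio Baseline_Age Baseline_AGV"
- 14.5.1, body proportion ratios: "Baseline_Age Baseline_AGV Baseline_Height_Z"

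The fifth, in 14.5.2, has "Baseline_*growth_measure* Baseline_AGV Baseline_Height_Z-score Treatment" and stratum, without age. It serves ten measures: nine recorded lengths or circumferences plus the derived lower body length. Neither 14.5.2 nor the change summary in SAP section 22 comments on the absence of age. SAP 14.5 states that p-values for this group of endpoints are non-confirmatory.

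**The concern.** The omission looks like a slip rather than a choice. The ratios in 14.5.1 are adjusted for age, while the lengths that form them, one subsection later, are not. Section 14.5.2 tabulates the same measures by baseline age category. The imputation model in 14.3.2, which 14.5.2 borrows for missing standing and sitting height, also uses age. The LSMEANS line in 14.5.2 is also written differently from the other four: it requests all differences and does not name placebo as control. That suggests, without proving, that the block was not harmonised. Age was also once a design factor: "In the original protocol, subjects were stratified based on sex and age" (SAP 4.6.2). The current stratum variable holds only sex and Tanner stage.

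What is at stake is precision. Growth over a year may depend on age, and a prognostic baseline covariate that is already collected but left out of the model leaves avoidable residual variance in the treatment comparison.

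**Working it through.** **The plan's own figure.** The documents give no precision or power figure for these models. The only power statement is for AGV (Protocol 14.6, SAP 4.5): 55 per arm, difference 1.75 cm/year, SD 2.80, two-sided 0.05. The standardised difference is 1.75 / (2.80 × √(2/55)) = 3.28. This gives power 0.906 by the normal approximation and 0.901 by the noncentral t with 108 df, which agrees with the stated 90%. The AGV model contains age, so this figure is unaffected.

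**How much of age the 14.5.2 model already carries.** Under SAP 14.4.1, "Each measurement of standing height will be converted to an age-and sex-appropriate standard deviation score". Standing height, its Z-score and sex therefore nearly fix age. The other nine models contain the Z-score, from which age has been removed, but not height itself. Age enters them mainly through the baseline measure, and partly through baseline AGV and Tanner stage.

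**Assumptions (not in the documents).** 110 subjects, 1:1, with age uniform over 5-15 or 5-18 and 20% above Tanner stage I. Reference height is 109 cm at age 5 plus 6 cm per year, with reference SD 4.7 cm plus 0.15 or 0.35 cm per year. Height Z-score has mean -5 and SD 1. Baseline AGV falls 0.15 cm/yr per year of age. The baseline measure is height itself, or a variable correlated 0.95, 0.80 or 0.50 with height. The outcome has an age slope b of 0.1, 0.2 or 0.3 residual SD per year. The 14.5.2 model was fitted with and without age, 1000 runs per setting.

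**Results, ages 5-15.** R² is for age on the other covariates. The last three columns give the SE of the treatment difference without age divided by the SE with age.

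| Baseline measure | R² | b = 0.1 | b = 0.2 | b = 0.3 |
|---|---|---|---|---|
| Standing height | 0.994-0.999 | about 1.00 | about 1.00 | about 1.00 |
| Correlation 0.95 | 0.89-0.91 | 1.00 | 1.01 | 1.04 |
| Correlation 0.80 | 0.71-0.74 | 1.01 | 1.05 | 1.11 |
| Correlation 0.50 | 0.54-0.58 | 1.02 | 1.08 | 1.17 |

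For standing height the exact range over all settings is 0.995-0.999.

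**Hand check.** Ratio ≈ √(1 + b²V(1 − R²) × 110/103) × √(1 − 1/102). V is the variance of age, 10²/12 = 8.33. The factor 110/103 allows for the seven terms fitted to age. The last factor, 0.995, is the price of one more covariate. At b = 0.2, b²V = 0.333, and with the lower R² in each row:

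- R² = 0.89: √(1 + 0.333 × 0.117) × 0.995 = 1.014
- R² = 0.71: √(1 + 0.333 × 0.310) × 0.995 = 1.045
- R² = 0.54: √(1 + 0.333 × 0.491) × 0.995 = 1.073

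These agree with the simulated column to within 0.01.

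**What the slopes imply.** Age alone explains b²V / (1 + b²V) of the outcome variance. That is 0.083/1.083 = 8% at b = 0.1, 0.333/1.333 = 25% at 0.2 and 0.75/1.75 = 43% at 0.3. For ages 5-18, V = 13²/12 = 14.08, and b = 0.3 implies 1.27/2.27 = 56%. In that setting the ratios reach 1.06, 1.17 and 1.25 for the three correlations. These are extreme assumptions.

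**In subjects.** A ratio r is equivalent to losing 1 − 1/r² of the sample: 9% at 1.05 (10 of 110) and 14% at 1.08 (16 of 110).

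**The case against.** The best defence is that no rule is broken. SAP 14.1 allows exceptions, and an explicit MODEL statement is one. That stands: a reader might infer that the SAP contradicts itself, and it does not. The change summary records differences from the previous SAP version, so its silence proves little if 14.5.2 was never altered.

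A second defence is that this model alone adjusts for a raw body size, which itself carries age, whereas the other four adjust for a velocity, a Z-score or a ratio. This is decisive for standing height and nearly so for measures that track height closely, as sitting height and lower body length may. It is weaker for head circumference or single limb segments, and the SAP does not offer it as a reason.

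Third, the size of the loss is assumed, and the simulation puts the whole age effect directly on the outcome, with none of it running through AGV, Tanner stage or body size. That favours finding a loss. It is why the losses of 17% and 25% should not be read as expected values.

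A reader might also infer bias, particularly because age was an early stratification factor. The documents do not support this: treatment was randomised, so omitting a baseline covariate does not bias the difference. SAP 4.6.2 does not say how many subjects were randomised under the age strata, and it specifies that analyses use sex and Tanner stage.

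**Conclusion.** The point holds as a minor one. Age is missing from one of five coded ANCOVAs, against the SAP's own default and without explanation. No primary or key secondary result is affected.

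For standing height the loss is nil. For the other nine measures the plausible cost is a standard error up to about 8% larger, and close to zero where the measure follows height. This rests on assumed slopes of 0.1-0.2 residual SD per year, ages 5-15 and correlations with height of 0.50-0.95. Larger losses need age alone to explain some 43-56% of the outcome variance. The omission itself is certain; the size of the precision loss cannot be fixed from the documents.

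**What to change.** Add Baseline_Age to the single MODEL statement in SAP 14.5.2 and use it for all ten measures, which brings the section into line with 14.1. One common statement is simpler than separate models for standing height and the rest.

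The cost is one degree of freedom and no new data. For standing height, where age is nearly redundant, the standard error of the treatment difference would widen by about 0.1-0.5% (the inverse of the 0.995-0.999 ratio).
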